4. PARTICIPANT DISPOSITION

4.1. Participant Enrollment and Disposition

A summary of participant enrollment will be provided for each country, investigator within a country, and overall. The summary will present the number and percentage of participants enrolled. For each column, the denominator for the percentage calculation will be the total number of participants analyzed for that column.

A summary of participant disposition will be provided by overall. This summary will present the number of participants screened, the number of participants who met all eligibility criteria but were not enrolled with reasons for participants not enrolled, the number of participants enrolled, and the number of participants in each of the categories listed below:

- Full Analysis Set
- Safety Analysis Set
- Completed study drug
- Did not complete study drug with reasons for premature discontinuation of study drug
- Completed study
- Did not complete the study with reasons for premature discontinuation of study.

For the status of study drug and study completion and reasons for premature discontinuation, the number and percentage of participants in each category will be provided. The denominator for the percentage calculation will be the total number of participants in the Safety Analysis Set corresponding to that column. In addition, a flowchart will be provided to depict the disposition.

The following by-participant listings will be provided by participant identification (ID) number in ascending order to support the above summary tables:

- Participant disposition, including, date of enrollment, first dose date and day, last dose date and day, end of study date and day, study drug discontinuation, study discontinuation, and reasons for study drug or study discontinuation.
- Reasons for screen failure (will be provided by screening ID number in ascending order).

4.2. Extent of Study Drug Exposure and Adherence

Extent of exposure to study drug will be examined by assessing the total duration of exposure to study drug and the level of adherence relative to the study drug regimen specified in the protocol.

4.2.1. Duration of Exposure to Study Drug

Total duration of exposure to study drug will be defined as last dosing date minus first dosing date plus 1, regardless of any temporary interruptions in study drug administration, and will be expressed in weeks using up to 1 decimal place (eg, 4.5 weeks). If the last study drug dosing date is missing, the latest date among the study drug end date, clinical visit dates, laboratory sample collection dates, and the vital signs assessment dates that occurred during the on-treatment period will be used for that participant included in the final analyses.

The duration of exposure to study drug will be summarized using descriptive statistics (n, mean, SD, median, Q1, Q3, minimum, and maximum) and as the number and percentage of participants exposed for specified periods, eg, \geq 4 weeks (28 days), \geq 8 weeks (56 days), \geq 12 weeks (84 days), \geq 24 weeks (168 days), etc.

Summaries will be provided by overall participants for the Safety Analysis Set.

No formal statistical testing is planned.

4.2.2. Adherence to Study Drug

Study drug regimen adherence will be computed based on pill counts. The numbers of pills of study drug B/F/TAF dispensed and returned are captured on study drug accountability eCRF.

Adherence (%) of B/F/TAF will be calculated as follows:

$$\begin{aligned}\text{Adherence}(\%) &= 100 \times \frac{\text{Total No. of pills taken}}{\text{Total No. of pills prescribed}} \\ &= 100 \times \frac{\sum \text{No. of pills taken at each dispensing period}^{[1]}}{\sum \text{No. of pills prescribed at each dispensing period}^{[2]}}\end{aligned}$$

[1] Number of pills taken at a distinct dispensing period for a study drug is calculated as the minimum of (a) the daily number of pills prescribed for the study drug multiplied by the duration of treatment at the dispensing period, and (b) the number of pills taken for the study drug (number of pills dispensed minus the number of pills returned). Total number of pills taken is determined by summing the number of pills taken from all evaluable dispensing periods.

[2] Number of pills prescribed at a distinct dispensing period for a study drug is calculated as the daily number of pills prescribed for the study drug multiplied by the duration of treatment at the dispensing period. Total number of pills prescribed is determined by summing the number of pills prescribed from all evaluable dispensing periods

The duration of treatment at a dispensing period for a study drug is calculated as the minimum of (a) the last returned date of study drug at a dispensing period, (b) date of premature discontinuation of the study drug, and (c) next pill dispensing date of the study drug, minus dispensing date of the study drug.

The next pill dispensing date is the following dispensing date of the study drug regardless of the bottle return date.

For a record where the number of pills returned was missing (with “Yes” answered for “Was Bottle returned?” question), it is assumed the number of pills returned was zero. If the number of pills dispensed was missing or any study drug bottle was not returned, or the bottle return status was unknown, then all records in that dispensing period for that study drug will be excluded from both denominator and numerator calculation.

Overall adherence to study drug will be calculated using all data from the entire dosing period up to the date of permanent discontinuation of the study drug for participants who prematurely discontinued study drug or completed study drug.

Adherence up to Week 12 will be calculated using all data from the entire dosing period up to the date of permanent discontinuation of the study drug for participants who prematurely discontinued study drug or completed study drug, or the Week 12 study drug dispensing date, whichever occurs earliest.

Descriptive statistics for overall adherence and adherence up to Week 12 for the study drug (n, mean, SD, median, Q1, Q3, minimum, and maximum) along with the number and percentage of participants belonging to adherence categories (e.g., < 80%, ≥ 80 to < 90%, ≥ 90% to < 95%, ≥ 95%) will be provided for the Safety Analysis Set. No formal statistical testing is planned.

A by-participant listing of study drug administration will be provided by participant ID number (in ascending order) and visit (in chronological order).

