Study Drug Accountability		X	X	X	X	X	X	
Study Drug Dispensation		X		X				
Observed Dosing		X	X	X				Participants must take their study drug in the clinic for observed dosing on Day 1, Week 4, and Week 12.

CBC = complete blood count; CD4+ = clusters of differentiation 4; DNA = deoxyribonucleic acid; DBS = dried blood spot; ESDD = early study drug discontinuation; GFR = glomerular filtration rate calculated using the Cockcroft-Gault equation; HBV = hepatitis B virus; HCV = hepatitis C virus; HIV-1 = human immunodeficiency virus type 1; HIVTSQs = HIV treatment satisfaction status questionnaire [quantitative]; HIVTSQc = HIV treatment satisfaction change questionnaire [quantitative]; RNA = Ribonucleic acid; PK = pharmacokinetic(s); TFV-DP = tenofovir diphosphate.

- a Evaluations to be completed within 42 days prior to Day 1 visit.
- b Participants will be dispensed study drug at the Day 1 visit; initiation of treatment with the study drug must take place in the clinic for observed dosing at Day 1 visit.
- c All study visits are to be scheduled relative to the Day 1 visit date. Visit windows are  $\pm 2$  days of the protocol-specified date through Week 12,  $\pm 6$  days of the protocol-specified date for Week 24. For the purpose of scheduling a 30-day follow-up visit, a  $\pm 6$ -day window may be used. Those participants who prematurely discontinue study drug and continue in the study through at least one subsequent visit after the early study drug discontinuation visit will not be required to complete the 30-day follow-up visit.
- d Only applies to participants who miss the Week 24 visit, and must be completed within 30 days of discontinuing study drug.
- e Early study drug discontinuation visit to occur within 72 hours of last dose of study drug.
- f Chemistry profile: alkaline phosphatase, AST, ALT, total bilirubin, direct and indirect bilirubin, total protein, albumin, bicarbonate, BUN, calcium, chloride, creatinine, glucose, potassium, and sodium.
- g For any post-Day -1 visit, if the HIV-1 RNA value is  $\geq 50$  copies/mL, a retest should be performed at a scheduled or unscheduled visit 2-4 weeks after the date of the original test.

- h Hepatitis B virus surface Antigen (HBsAg), Hepatitis B core antibody (HBcAb), and Hepatitis C virus (HCV) serologies (reflex HCV RNA is performed in participants with positive HCV Ab serology)

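### SAP 4.2.2 leaves one due dose out of the adherence denominator when the final dispensing period ends on a dosing day, and gives two conflicting end points for completers

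*SAP*

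**What the plan says.** SAP 4.2.2 computes adherence as pills taken over pills prescribed, summed over dispensing periods. Pills prescribed are the daily number times the length of the period. The period ends at the earliest of three dates. The first is when bottles were last handed back; the other two, and the subtraction, read "b) date of premature discontinuation of the study drug, and (c) next pill dispensing date of the study drug, minus dispensing date". Pills taken in a period cannot exceed pills prescribed, because they are set to "the minimum of (a) the daily number of pills prescribed for the study drug multiplied by the duration of treatment at the dispensing period" or the net pill count, whichever is smaller.

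The same section then says that overall adherence uses data "up to the date of permanent discontinuation of the study drug for participants who prematurely discontinued study drug or completed study drug". The Week 12 figure adds a further limit: "or the Week 12 study drug dispensing date, whichever occurs earliest".

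SAP 4.2.1 measures the same kind of span differently: "Total duration of exposure to study drug will be defined as last dosing date minus first dosing date plus 1". SAP 3.7.1 defines a Last Dose Date for participants who stopped early and for those who completed, but SAP 4.2.2 does not refer to it.

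Protocol Table 3 dispenses drug at Day 1 and Week 12 only. It schedules accountability at Week 24 and also at the 30-day follow-up visit, whose footnote reads "Only applies to participants who miss the Week 24 visit, and must be completed within 30 days of discontinuing study drug".

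**The concern.** A plain date difference is the right count of due doses when a period ends at the next dispensing, provided that day's dose comes from the new bottle. The final period has no next bottle. If the last dose is taken on the end date, both the first and the last day of the period are dosing days, and the difference is one short. The cap then limits pills taken to that short count, so one missed dose disappears.

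The second problem is the end date for completers. Limit (b) concerns premature discontinuation and limit (c) does not exist after Week 12. Read alone, the length rule therefore runs to the bottle return, and off-drug days count as prescribed doses. The later sentence on permanent discontinuation points the other way, and the section does not say which governs.

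Adherence is reported in categories (below 80%, 80 to below 90%, 90 to below 95%, and 95% or more) and is useful context for bictegravir troughs and any viral rebound. With about 35 participants, one person in the wrong category moves it by 1/35, or 2.9 points.

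**Working it through.** The plan states no adherence figure, so there is none to reproduce.

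Inputs from the documents: one tablet daily from Day 1 (Protocol 5.4); dispensing at Day 1 and Week 12 (Protocol Table 3); nominal Days 84 and 168 for Weeks 12 and 24 (SAP Table 3-1). Assumed: stop dates, return dates, missed-dose counts, and a Week 12 clinic dose taken from the new bottle.

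**Early stopper in the first period, last dose on the stop date.** Let N be the dosing days, first to last inclusive, and k the missed doses.

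- Reported: min(N − 1, N − k) / (N − 1). True: (N − k) / N.
- k = 0: the cap gives (N − 1)/(N − 1) = 100%, which is correct.
- k ≥ 1: the excess is (N − k)/(N(N − 1)), largest at k = 1, where it equals 1/N.

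| N | k | Reported | True | Excess (points, unrounded inputs) |
|---|---|---|---|---|
| 14 | 1 | 13/13 = 100% | 13/14 = 92.9% | 7.1 |
| 28 | 1 | 27/27 = 100% | 27/28 = 96.4% | 3.6 |
| 28 | 3 | 25/27 = 92.6% | 25/28 = 89.3% | 3.3 (crosses 90%) |
| 56 | 3 | 53/55 = 96.4% | 53/56 = 94.6% | 1.7 (crosses 95%) |
| 1 | 0 | 0/0 | 1/1 = 100% | undefined |

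If the stop date is recorded as the day after the last dose, the length is N and the error vanishes: N = 28, k = 3 gives 25/28 = 89.3%.

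**Completer returning bottles on Day 168.** The lengths are (84 − 1) + (168 − 84) = 83 + 84 = 167.

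- Last dose Day 168, 1 missed in the final period: 167/167 = 100% against 167/168 = 99.4%, an excess of 0.6 points.
- Last dose Day 168, 9 missed, all in the first period: (74 + 84)/167 = 94.61% against 159/168 = 94.64%, a shortfall of 0.03 points.
- Last dose Day 167: 167 doses were due, so there is no error.

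**Fully adherent completer, last dose Day 168, bottles returned L days later (L ≥ 1).**

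- Length rule alone: (83 + 85)/(83 + 84 + L) = 168/(167 + L). L = 14 gives 168/181 = 92.8%; L = 30 gives 168/197 = 85.3%. The result is below 95% from L = 10 (168/177 = 94.9%) and below 90% from L = 20 (168/187 = 89.8%).
- With the permanent-discontinuation sentence applied, ending on Day 168: (83 + min(84, 85))/(83 + 84) = 167/167 = 100%.

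**Week 12 adherence.** For a participant who reaches Week 12, the length is 83 and the doses due on Days 1 to 83 are 83, so nothing is lost. A participant who stops before Week 12 carries the error in the table.

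**The case against.** The strongest reply is that the error is conditional and small. It needs the last dose to fall on the end date. SAP 4.2.2 does not say that the discontinuation date is the last dose date, and if it is the following day the count is right. For completers, a clinic dose on the return day is not certain either. Protocol 6.3.6 calls for a witnessed dose with a 2-hour sample at Week 24, but the observed-dosing row of Table 3 lists only Day 1, Week 4 and Week 12, and the approximately 10 French participants have no PK sampling. All of this stands, and it limits the point to the cases described.

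It can also be said that the completer question is already answered, because the sentence on permanent discontinuation names completers and SAP 3.7.1 gives them a Last Dose Date. That is a sensible reading. But the length formula, which a programmer would code, has no matching term, so the text still allows both results. Late return is an assumed case: accountability is scheduled at Week 24, and the 30-day visit applies only to those who miss it.

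Finally, adherence is descriptive and feeds no endpoint, test or analysis set. That is correct and fixes the priority of the change. It does not make the formula right.

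**Conclusion.** The point holds as a small, correctable error plus an ambiguity. When the final period ends on a dosing day, one due dose is dropped and one dose missed in that period is hidden. The overstatement is at most 1/N for an early stopper and about 0.6 points for an on-time completer; a single Day 1 dose has no defined value. For completers, two instructions in one section need reconciling, since a 30-day-late return gives about 85% or 100%. The sizes rest on the assumed dates and missed-dose counts.

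Four stronger readings are not supported:

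- A reader might infer that every participant loses a day. None is lost when a period ends at the next dispensing, or when the stop or return date is after the last dose. A completer who returns late and is measured by the length rule alone has a denominator that is too long.
- A reader might infer that all early stoppers look better than they were. Those who missed no dose read 100% correctly, apart from the undefined Day 1 case.
- A reader might infer that adherence is understated for late-returning completers. The text does not settle this, because the later sentence gives the correct 100%.
- A reader might infer that pill count is the only adherence measure for all participants. Question 5 of the Week 4 questionnaire asks about missed doses and is summarised for all sites (SAP 3.3 and 9.2.2). Pill count is the only summary covering all 24 weeks.

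**What to change.** In SAP 4.2.2, define the length of each dispensing period, for completers and early stoppers alike, as

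min(Last Dose Date per SAP 3.7.1, last returned date, next dispensing date − 1) − dispensing date + 1.

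Checks on the examples: N = 28 gives 28/28 = 100%, 27/28 = 96.4% and 25/28 = 89.3% for 0, 1 and 3 missed doses. A single Day 1 dose gives 1/1. The completer with all 168 doses gives (83 + 85)/168 = 100% for a return on Day 168 or any later day. With continuous supply, the lengths add up to the SAP 4.2.1 exposure duration.

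The SAP should also state which bottle supplies the Week 12 clinic dose. If it is the old one, the first-period cap makes a fully adherent completer read (83 + 84)/168 = 99.4% under this rule. The Week 24 dosing statements in Protocol 6.3.6 and the observed-dosing row of Table 3 should be reconciled.

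The cost is one sentence in the SAP and one line of programming. No new data are needed and no endpoint changes.

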4.3. Protocol Deviations

If there are any participants did not meet the eligibility criteria for study entry but enrolled in the study, then will be summarized regardless of whether they were exempted by the sponsor or not. The summary will present the number and percentage of participants who did not meet at least 1 eligibility criterion and the number of participants who did not meet specific criteria by treatment group based on the All Enrolled Analysis Set. A by-participant listing will be provided for those participants who did not meet at least 1 eligibility (inclusion or exclusion) criterion. The listing will present the eligibility criterion (or criteria if more than 1 deviation) that participants did not meet and related comments, if collected.

Protocol deviations occurring after participants entered the study are documented during routine monitoring. The number and percentage of participants with at least 1 important protocol deviation will be summarized by deviation category for the All Enrolled Analysis Set as appropriate. The total number of important protocol deviations will be summarized by deviation category A by-participant listing will be provided for those participants with protocol deviations, included a column specify whether the protocol deviation is important.

5. BASELINE CHARACTERISTICS

5.1. Demographics and Baseline Characteristics

Participant demographic variables (ie, age, sex, gender identity, sexual orientation, race, and ethnicity) and baseline characteristics (body weight [in kg], height [in cm], body mass index [BMI; in kg/m²]) will be summarized by overall using descriptive statistics for continuous variables and using number and percentage of participants for categorical variables. The summary of demographic data will be provided for the Safety Analysis Set. Missing values will not be included in the denominator when calculating percentages.

A by-participant demographic listing, including the informed consent date, will be provided by participant ID number in ascending order.

5.2. Other Baseline Characteristics

The following baseline disease characteristics will be summarized by overall using descriptive statistics for continuous variables and using number and percentage of participants for categorical variables.

- HIV-1 RNA categories (copies/mL): (a) < 50, (b) ≥ 50
- CD4 cell counts (/uL)
- CD4 cell counts categories (/uL): (a) < 50, (b) ≥50 to < 200, (c) ≥ 200 to < 350, (d) ≥ 350 to < 500, and (e) ≥ 500
- CD4 percentage (%)
- Mode of infection (HIV infection risk factors)
- HIV disease status: AIDS, asymptomatic, or symptomatic HIV infection
- eGFR_{CG} (mL/min)
- HBV Surface Antigen Status
- HBV Core Antibody Status
- HCV Antibody Status
- Duration of baseline CAB+RPV exposure (year)
- Time between last dose date of baseline CAB+RPV and first dose date of study drug (days)
- Historical HIV-1 genotype resistance results: INSTI (Yes/No/Data Not Available), NNRTI (Yes/No/Data Not Available), NRTI (Yes/No/Data Not Available), PI (Yes/No/Data Not Available).

These baseline characteristics will be summarized using descriptive statistics (n, mean, SD, median, Q1, Q3, minimum, and maximum) for continuous data and using number and percentage of participants for categorical variables. The summary of these baseline characteristics will be provided for the Safety Analysis Set. No formal statistical testing is planned.

A by-participant listing of other baseline characteristics will be provided by participant ID number in ascending order.

5.3. Medical History

Medical history will be collected at screening. Medical history will be coded using the current Medical Dictionary for Regulatory Activities (MedDRA) dictionary.

A by-participant listing of medical history will be provided for all participants by participant ID number in ascending order.

6. EFFICACY ANALYSES

Efficacy data will be summarized for the participants in the FAS. For the FAS, all efficacy data, including data collected after the last dose of study drug, will be included, unless specified otherwise.

